To date, only one smokeless tobacco cessation intervention (Enough Snuff) has been empirically tested and found effective at helping smokeless tobacco users quit. Jitnarin et al recently beta tested QUIT SPIT, a culturally tailored version of the 54-page adaption of the Enough Snuff booklet specific for firefighters and found the intervention to be feasible and acceptable among those who wanted to quit. Firefighters indicated that delivery of the messages via an mHealth platform (app or website) may be preferable to the printed version, supporting the significance of our proposed study. Our current intervention is testing an mHealth intervention delivering scheduled gradual reduction (SGR) and supportive text messages to smokeless tobacco users interested in quitting. The SGR program has users reduce the number of dips per day over 6 weeks by lengthening the interval between dips based on a set algorithm. SGR helps mitigate withdrawal symptoms commonly experienced among highly dependent chewers by providing even spacing between dips. Further, SGR helps chewers self-regulate their behavior and practice restraint strategies in response to tobacco use cues during the reduction period prior to quitting. We have enrolled 12 firefighters in the parent EnufSnuff study to date. Initial reactions to the intervention are positive; however, delivery of SGR to participants who work in shifts such as firefighters and EMTs is problematic. Firefighters work a 10-day cycle with alternating 24-hours shifts for 6 days and then 4 days off. Other first responders also work in shifts. Their work also might remove the possibility to dip if they are out on an emergency call. This schedule may be a barrier to effective engagement with the SGR program. Through our preliminary work, we have also identified cultural norms regarding cancer risk and risk behaviors that could be addressed via supportive text messages. More research is needed to develop an mHealth intervention to meet the unique needs of first responders, such as firefighters and EMTs who are interested in quitting smokeless tobacco.

mHealth interventions have the potential to increase the reach and engagement of Firefighters in cessation interventions

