mHealth interventions for tobacco cessation have potential to facilitate participant engagement and activation by reaching people in the real-world setting. Previous research indicates that features which promote engagement (e.g., interactive text messaging) are positively associated with quit rates. Following a user-centered design approach and getting input from the target audience is essential for developing mHealth interventions that are efficacious and usable. Many mHealth behavior change interventions are designed without users in mind thus limiting their potential efficacy. Our proposed study will engage firefighters throughout the development process to ensure that the intervention is developed to meet their cessation needs. Thus, the potential impact and reach of a user developed, mHealth intervention warrants investigation in helping firefighters quit.

Summary

First responders, such as firefighters and paramedics / EMTs, who use smokeless tobacco represent a group vulnerable for tobacco use. Despite their high risk for both tobacco-related and occupational-related cancers, this group of smokeless tobacco users has not been widely targeted for cessation intervention trials. There are very few interventions available tailored to the unique needs of firefighters, and there are currently no mHealth interventions that address smokeless tobacco cessation for this population. mHealth interventions have the potential to consistently reach and consistently engage many more firefighters who use smokeless tobacco given their varying work schedules, and this approach warrants testing in this population. Our proposed study will develop and pilot a mHealth intervention to address the unique cessation needs of firefighters who use smokeless tobacco. If successful, this pilot will serve as the basis for a larger trial to test the efficacy of this intervention on a larger scale. The proposed study has public health relevance in that the goal is to decrease cancer risk among firefighters by increasing access and uptake of tobacco cessation interventions in an understudied group of tobacco users.

Design & Procedures

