Text-based Cessation Support Intervention: Participants will receive text-based support messages 2-3 times per day over ten weeks. The messages are based on constructs of Social Cognitive Theory the Health Belief Model and the Theory of Self-regulation. Messages were developed from our pilot work with firefighters and address salient features that are associated with smokeless tobacco use in this population such as stress. The text-based system with have interactive capabilities, participants can text the word CRAVE if they are having a craving and will receive a message to help them deal with the craving. Participants can also text the word SLIP if they have a slip after their quit date and will receive a message to get them back on track. Participants can text MOOD if they need a positive message to boost their mood. Finally, participants can text the word CALL, a feature that can be used to address the stress that is commonly felt post-call. Messages will focus around providing mindfulness and deep breathing activities to deescalate after participating in a call.

Nicotine Replacement Therapy: We will provide participants via mail nicotine replacement the nicotine lozenge at no cost. We will provide a 4 week supply of 4mg Lozenge (mirroring the dose and the length to similar studies with smokeless tobacco users) with instructions on how to use. Participants will be instructed via text to start their NRT on their quit date. Participants will be instructed to use the lozenges every day for 12 weeks. For the first 6 weeks, use 1 lozenge every 1-2 hours. For the next three weeks, use 1 lozenge every 2-4 hours. For the last three weeks, use 1 lozenge every 4-8 hours. They should not use more than 5 lozenges in 6 hours, or more than 20 lozenges total per day. For any side effects potentially related to use of the nicotine replacement, we will instruct participants to stop using the lozenge and contact the study phone number to speak to a registered nurse (PI is a registered nurse). We will explain side effects that include nausea, light-headedness, headache, poor sleep, mouth sores and heart palpitations. We will explain that severe side effects (vomiting, syncope, tachycardia) related to use of the nicotine replacement are rare; however, we will make participants aware of these and will instruct them to contact the PI (a registered nurse) if they occur.

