Feasibility. The feasibility outcomes will be: (a) the number of smokeless tobacco users recruited and randomized during the 4-month recruitment period; (b) engagement in the intervention measured by the portion of responses to messages that require a response; (c) the retention rates in the mHealth intervention compared to the control group at 30-days post intervention completion. We will determine

the feasibility by: (a) ability to recruit and enroll 50 participants in 4-months; (b) engagement with the intervention by having participants respond to at least 75% of messages or engage with 75% of the content using both self-report and objective methods. To calculate the proportion of messages read per participant, we will use a 5-point Likert scale to ask participants the following questions: "What did you typically do when you received a message from the mHealth intervention?" (1= ignored it completely, 5= read it immediately), "On a typical day, did you read messages you received?" (1= Not at all, 5= read the entire message), and On a typical day, did you engage with the intervention you received?"(1= Not at all, 5= read the entire message); and (c) ability to retain 80% of the sample at the 30-days follow-up. All participants will be given the option to participate in a phone interview with a member of the study team to expand on these answers approximately 1 month after their intervention has completed.

Acceptability and Consumer Satisfaction. To determine acceptability, we will ask the following questions using a 5-point Likert scale tailored to each arm of the study: 1) How useful was the intervention in helping you to quit smokeless tobacco (1 - Not at all useful, 5 = Extremely useful); 2) whether the intervention will change their smokeless tobacco use (1= Will not change at all, 5 = Will change a lot); 3) Did the intervention make you think about quitting (1= Not at all; 5 = All the time); and 4) Would you recommend the program to a friend (1 = Definitely would not recommend, 5 = Definitely would recommend). We will deem the pilot "acceptable" if each question has a mean level of 4 or higher.

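### The self-report engagement item is anchored on reading, item 1 mixes reading with promptness, and the plan does not say whether keyword texts count as engagement

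*Combined protocol and SAP*

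**What the plan says.** Design & Procedures makes feasibility a primary outcome and includes in it the ability to engage firefighters in the mHealth intervention. Measures, Feasibility defines this component as "engagement in the intervention measured by the portion of responses to messages that require a response". The success criterion there is a response to at least 75% of messages, or engagement with 75% of the content, by self-report and objective methods together.

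Three self-report items on a five-point scale follow. They are introduced as the way to work out what share of messages each participant read.

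- Item 1 asks what the participant typically did on receiving a message: "1= ignored it completely, 5= read it immediately".
- Item 2 asks about reading: "On a typical day, did you read messages you received?' (1= Not at all, 5= read the entire message".
- Item 3 asks about engagement: "and On a typical day, did you engage with the intervention you received?'(1= Not at all, 5= read the entire message".

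The Text-based Cessation Support Intervention section describes four keywords that the participant starts. For example, "participants can text the word CRAVE if they are having a craving and will receive a message to help them deal with the craving". SLIP, MOOD and CALL work in the same way, and CALL is meant for stress after an emergency call. Neither Measures nor Data Analysis & Statistical Considerations mentions keyword use. The latter says only that engagement will be described.

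**The concern.** An item that asks about engaging should separate people who interact from people who only read. Item 3 cannot, because its top answer is about reading. The keywords are the part of the intervention that the participant starts, and no engagement measure names them.

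The Background section says that "features which promote engagement (e.g., interactive text messaging) are positively associated with quit rates", and the pilot is meant to be the basis for a larger trial. If the self-report score reflects reading alone and keyword use goes unreported, a favourable engagement result would say little about whether these features were used.

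**Working it through.** The plan states no figure on this point, so there is none to reproduce. The check compares the texts and then gives an illustration under stated assumptions.

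**Step 1. Question against top anchor (Measures, Feasibility).**

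| Item | Asks about | A score of 5 means | Fits its own question? | Fits the purpose (share read)? |
|---|---|---|---|---|
| 1 | usual reaction to a message | read at once | yes | no, adds promptness |
| 2 | reading | read in full | yes | yes |
| 3 | engaging | read in full | no | only by repeating item 2 |

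**Step 2. Objective side.** The defined measure counts replies to messages that require one. In the mHealth arm, the only text described as asking for a reply is the end-of-day dip count, and it belongs to the Reduction Cessation path. None is described for Abrupt Cessation, although the final content may contain some. A keyword text is not a reply to a prompt, and it has no fixed number of occasions from which to form a percentage. The content part of the criterion might cover keyword logs, but the plan does not say what content is or how it is measured.

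**Step 3. A reader who never interacts.** At 2-3 support texts a day over ten weeks, the count is 2 × 70 = 140 to 3 × 70 = 210. The Abrupt Cessation paragraph gives eight weeks of messages; at the same rate that is 2 × 56 = 112 to 3 × 56 = 168. A participant who reads all of them in full and sends nothing back scores 5 on item 2 and 5 on item 3, with a keyword count of 0. The length of the programme does not affect this.

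**Step 4. Effect on 75%, under assumed scoring.** The plan gives no conversion. Take m as the unweighted mean of the three items, and convert it by (m − 1)/4 or by m/5. The intermediate scores are also assumptions, since the plan labels only 1 and 5.

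| Participant | Items 1, 2, 3 | m | (m − 1)/4 | m/5 |
|---|---|---|---|---|
| Reads all at once, never interacts, item 3 as written | 5, 5, 5 | 15/3 = 5.00 | 100% | 100% |
| Same person, item 3 anchored on interaction | 5, 5, 1 | 11/3 = 3.67 | 67% | 73% |
| Reads all in full but late, item 3 as written | 3, 5, 5 | 13/3 = 4.33 | 83% | 87% |
| Later still, item 3 as written | 2, 5, 5 | 12/3 = 4.00 | 75% | 80% |

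If item 1 were used alone, a score of 3 gives 50% or 60%, and a score of 2 gives 25% or 40%.

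Under these rules, the anchor on item 3 decides which side of 75% a non-interacting reader falls. A late reader still reaches 75% on the three-item mean but not on item 1 alone. The result depends on a scoring rule that the plan does not state.

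**The case against.** The defence has several good points.

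- **The items are about reading by their stated purpose.** This justifies item 2's anchors. It does not rescue item 3, which asks about something else and, if reading is all that is wanted, adds nothing. Its anchors may be a copying slip; the correction is the same.
- **The outcome already captures interaction.** A reader might infer that the primary engagement outcome cannot see any interactive use. The documents do not support that. Prompted replies are two-way texting and are counted first, and the content part neither admits nor excludes keyword logs. What stands is that keyword use is unspecified.
- **On-call firefighters are not shown to be penalised.** A reader might infer that anyone who reads a text after a call is marked down and fails. Item 1 asks about typical behaviour, so an occasional delay does not rule out a 5. The Background remark "Their work also might remove the possibility to dip if they are out on an emergency call" concerns dipping; delayed reading is an inference from it and from the 24-hour shifts. Step 4 shows that failure does not follow. Only a habitual late reader is kept from 5, and only on item 1.
- **Keyword use depends on need.** Few CRAVE or SLIP texts may mean few cravings or slips. This stands, and it argues against any keyword threshold.
- **Nothing stops the team from reporting keywords.** The platform receives the texts, engagement is reported descriptively, and an optional phone interview is offered. So the documents do not show that the pilot would be unable to inform the larger trial. They show only that the plan does not commit to reporting this.

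**Conclusion.** The point holds in a limited form and is worth fixing. Item 3's anchor does not match its question and duplicates item 2. Item 1 answers its own question but brings timing into a calculation about share read. None of the four keywords is named in any engagement measure. Self-reported engagement could therefore come out high with no keyword use at all.

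The size of the effect on the 75% criterion cannot be given; the percentages above rest on assumed conversions and equal weights. Sample size, randomisation and the abstinence analysis are unaffected. The consequence is confined to how one component of the primary feasibility outcome is measured and read, in an arm of 25.

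**What to change.** 1. Re-anchor item 3 to interaction: how often the participant replied to a message or texted a keyword, from 1 = never to 5 = daily or more. If controls also receive the item, ask them about replies only, since no keywords are described for that arm.
2. Keep item 1 as a timing item and leave it out of the share-read calculation; use item 2 for that, and state how its rating is converted. Rewording item 1 to accept late reading would nearly duplicate item 2.
3. State that the reply portion decides the 75% criterion, and list the messages that require a reply on each quitting path so that the denominator is defined. If the content part is kept, say what it covers and how it is measured.
4. In Measures, Feasibility and in Data Analysis, Feasibility, add two descriptive figures for the mHealth arm from the text-platform log: the share of participants who sent at least one keyword, and the median keyword texts per participant, overall and by keyword. Report them beside the reply portion, with no threshold.

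The cost is one reworded survey item, a few sentences of text and one log export, with no added visits. The reworded item 3 combines replies and keywords, so the log is what separates them. Low keyword use will need cautious interpretation.

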Development of a M-Health Smokeless Tobacco Cessation Intervention for Firefighters

Document Date: 2/22/2024

NCT05111041

Purpose of the Study

The specific aims are:

Aim 1: In collaboration with the Professional Firefighters and Paramedics of North Carolina and our Advisory board of firefighters, develop a mHealth smokeless tobacco cessation intervention tailored to the specific needs of first responders such as firefighters and EMTs / paramedics. Using a co-facilitated user centered design approach and guided by the Spiral Technology Action Research Model (STAR) Model, we will work with firefighters & EMTS / paramedics to 1) identify and develop intervention content, messaging, and m-health modalities for delivery (e.g., text-messaging, text-chat); 2) refine the intervention; and 3) conduct usability testing. The outcome of Aim 1 will be a fully developed mHealth smokeless tobacco cessation intervention tailored to the unique needs of first responders (e.g., firefighters and EMTs) that is ready for pilot testing.

Aim 2: To assess the feasibility, acceptability, and preliminary efficacy of the tailored smokeless tobacco cessation intervention compared to a usual care control intervention in decreasing smokeless tobacco use. This aim will specifically address recruitment and retention to determine feasibility, acceptability as measured by the usefulness of the intervention received, and preliminary efficacy of the intervention in improving smokeless tobacco cessation at 30-days post intervention completion as measured by self-reported abstinence from smokeless tobacco use. This evaluation will be done with 50 firefighters & EMTs / paramedics who use smokeless tobacco who will be randomized to the tailored mHealth intervention (n=25) or the usual care control (n=25) of a self-help booklet. Both the intervention and control group will be given a 4 week supply of NRT lozenges with instructions of how to use.

Background & Significance

Firefighters are at high risk for cancer

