After gathering this feedback and incorporating it into the intervention design and content, we will present the updated intervention to the firefighters and EMTs in a second workshop to obtain their feedback on the design and content. We will use feedback to refine the intervention. We will then conduct usability testing during the third workshop. Usability testing will comprise: 1) observing smokeless tobacco users interacting with the intervention, guided by “concurrent think aloud” protocols, and taking field notes; and 2) gathering feedback through semi-structured interviews immediately following the use of the intervention. Overall usability of the intervention will be measured by adapting the System Usability Scale (SUS), a validated tool provided by the US Department of Health and Human Services, which consists of 10 items rated from “strongly disagree” to “strongly agree” (e.g., “I thought the intervention was easy to use” and “I felt very confident using the intervention”).

Aim 2: To assess the feasibility, acceptability and preliminary efficacy of the mHealth intervention compared to a usual care control intervention in decreasing smokeless tobacco use.

Objective: To determine if the mHealth intervention is feasible and acceptable for smokeless tobacco cessation for first responders such as firefighters and EMTs. We will also evaluate preliminary efficacy of the intervention in decreasing smokeless tobacco use.

Methods and Strategy:

Recruitment and Data Collection: We will recruit 50 smokeless tobacco users from collaborating Central North Carolina Fire Stations, and from social media ads that will run nationally in the United States. Inclusion criteria: 1) 18 years of age and older; 2) Employed as a professional firefighter or EMT / paramedic; 3) Have used smokeless tobacco for the last year and current (past 30 days) smokeless tobacco daily use; 4) Have access to a smart cell phone.

Randomization: Eligible participants will be randomized to either the mHealth Intervention (N=25) or control (N=25) group. Computerized randomization will be used to deliver a permuted block randomization with block sizes of four that will be used to randomly assign participants to one of the two intervention groups. The randomization scheme generated by the study statistician will be administered using the REDCap system.

Intervention:

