Preliminary Impact. We will measure 7-day point prevalence abstinence at 30-days post intervention. We will ask participants: "In the past 7 days, have you used any smokeless tobacco?" and the response will be code as no (0) or yes (1). We will also assess number of quit attempts and if they have been tobacco free for 7 days or more at any time during the intervention as secondary outcomes. Any participants that claim they have not used tobacco in 7 days will also be given the choice to opt into providing a saliva collection sample. Instructions to participants will be sent along with the sample collection kits. Samples will be discarded once the nicotine test has been performed.

Sample Characteristics and Other Explanatory Variables. In conjunction with the outcome measures, we will collect the following measures to describe the sample characteristics and obtain descriptive information regarding these concepts in this population. For this initial study, we want to explore the feasibility of obtaining these measures in this population and the current study design and examine the heterogeneity of the data.

Demographics. At baseline, we will assess age, gender, education, marital status, length of time as a firefighter or EMT and socioeconomic status (SES). Measures will be adapted from the study team's prior research.

Smokeless Tobacco Use History. At baseline participants will be asked about their smokeless tobacco use habit including: number dips/chews per day, age of initiation and number of past quit attempts and past use of other tobacco products including electronic cigarettes.

Nicotine Dependence-Smokeless Tobacco. At baseline we will assess nicotine dependence using the Severson Smokeless Tobacco Dependence Scale-Short Form (SSTDS). The SSTDS is a validated

questionnaire that has eight items with a range of scores from 0-19 with higher scores being most addicted to nicotine.

Readiness to Quit. At baseline participants will be asked to rate their readiness to quit using oral tobacco products. We will use an adaptation of the Contemplation Ladder for smokeless tobacco users that we have used extensively in our prior research, which are predictive of quitting tobacco. The participant uses a 1-10 scale to rate their readiness to quit, and we have found that a graphic ladder with anchors describing levels of readiness at several levels can be easily understood by participants.

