Cessation Resources. Participants in both arms will be asked if they accessed government sponsored cessation support services, other support for cessation (physician support) or any pharmacotherapy use at the 30-day follow-up.

Selection of Subjects

Study Sample.

We will target professional firefighters and EMTs who are smokeless tobacco users who live in the United States. Inclusion criteria will include: Inclusion criteria is: 1) 18 years of age and older; 2) Employed as a professional firefighter (may include volunteer firefighters and EMTs to reach those professionals who live in rural areas that do not have paid professionals); 3) Have used smokeless tobacco for the last year and currently (past 30 days) uses smokeless tobacco daily; 4) Have access to a smartphone.

Projected Enrollment.

We plan to recruit all participants for the current study using established connections between the study team and the Professional Firefighters and Paramedics of North Carolina who have expressed interest in working with us on the proposed study. We will also include in social media recruitment firefighters and EMTs from states within the USA. We will initially target two fire departments in Central North Carolina. Should we find that recruitment is still an issue and we need to expand to other local Fire Departments we will rely on our Advisory Board to identify other potential local Fire Departments to participate. Given this project was developed from an expressed need of firefighters we anticipate we will be able to recruit the sample necessary for this study.

Recruitment.

We will recruit 50 firefighters / EMTs who are smokeless tobacco users who live in the USA. Inclusion criteria: 1) 18 years of age and older; 2) Employed as a professional firefighter or EMT (interviews may include some volunteers in order to capture very rural areas that do not have paid professionals); 3) Have used smokeless tobacco for the last year and current (past 30 days) smokeless tobacco daily use; 4) Have access to a smart cell phone.

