Randomization: Eligible participants will be randomized to either the mHealth Intervention (N=25) or control (N=25) group. Computerized randomization will be used to deliver a permuted block randomization with block sizes of four that will be used to randomly assign participants to one of the two intervention groups. The randomization scheme generated by the study statistician will be administered using the REDCap system. We will also use a graded compensation for surveys with \$15 for baseline and \$20 for 30-days post end of program.

Risk/Benefit Assessment

This is a minimal risk study. The only risks are the potential for emotional distress in answering questions about smokeless tobacco use and the risk associated with smokeless tobacco use, and the potential loss of confidentiality. Every precaution will be taken to minimize these risks, including the ability to contact the PI for questions or concerns, and using encrypted devices to record PHI.

All participants may decline to be part of the study and may leave the study at any time without loss of benefit to which they are entitled.

The focus groups will be conducted in the firefighters' home station or individually via Zoom. Participants in focus groups will be familiar with each other and will be free to respond or not respond. Firefighters and EMTs will have the PI's email address and can message if they prefer to respond privately.

Intervention participants may choose the time and the place to take their surveys and respond or not respond to Mosio secure text messages. This will ensure their comfort with the privacy available to them. All study platforms will be secure and approved by Duke OIT, helping to ensure participant response confidentiality.

The potential benefits outweigh risks. Those who participate in the intervention have a high probability of benefitting if they decrease or cease using smokeless tobacco.

Data Analysis & Statistical Considerations

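### The follow-up item on pharmacotherapy does not separate study lozenges from outside medication, and no listed baseline item records cessation treatment already under way

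*Combined protocol and SAP*

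**What the plan says.** The Aim 2 eligibility lists (Recruitment and Data Collection; Selection of Subjects) cover age, occupation, tobacco use and a smartphone. The tobacco criterion is "Have used smokeless tobacco for the last year and current (past 30 days) smokeless tobacco daily use". No list mentions current cessation treatment, and the document has no exclusion criteria. All who qualify enter the trial: "Eligible participants will be randomized to either the mHealth Intervention (N=25) or control (N=25) group".

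The baseline measures named are demographics, tobacco history, dependence, readiness to quit and preferred quit method. The history covers "number dips/chews per day, age of initiation and number of past quit attempts and past use of other tobacco products including electronic cigarettes". None of these concerns cessation medication or support in use at entry.

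Outside help is asked about only at follow-up (Measures, Cessation Resources). The item covers public cessation services, other support such as a physician's, and "any pharmacotherapy use at the 30-day follow-up".

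The study itself supplies pharmacotherapy: "Both the intervention and control group will be given a 4 week supply of NRT lozenges" (Purpose of the Study, Aim 2). The Nicotine Replacement Therapy paragraphs for both arms tell participants to use the lozenges daily for 12 weeks. No separate measure of study-lozenge use is described.

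**The concern.** A participant who follows the lozenge instructions can truthfully answer yes to the pharmacotherapy question whether or not they used anything else. Once collected that way, the answer cannot be taken apart afterwards.

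Timing is lost as well. Treatment that began before randomisation is a baseline characteristic. Treatment that began afterwards may be a response to the assigned arm, for instance control participants looking for more help. With no baseline value and no start date, the plan cannot tell these apart for any of the three kinds of help.

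The stake is interpretation. The comparison is mHealth plus lozenge against booklet and texts plus lozenge, in 25 people per arm with few expected quitters. A reader of the results will want to know whether outside treatment differed between arms. The plan lists these measures to describe the sample and to learn whether they can be collected. As specified, this part of the item does neither well.

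**Working it through.** **1. The plan's own figure.** The Power Analysis gives quit rates of 12%-20% (mHealth) and 5%-10% (control), 25 per arm, and says power is below 80% at 0.05. With the normal approximation, power = Φ{[√n·|p1−p2| − 1.96·√(2p̄(1−p̄))] / √(p1(1−p1)+p2(1−p2))}, two-sided:

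- 12% v 5%: 14% (Fisher's exact test 3%)
- 12% v 10%: 4% (1%)
- 20% v 5%: 36% (20%)
- 20% v 10%: 16% (9%)

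The statement is confirmed. The present point does not change it.

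**2. Scale of the comparison.** Expected quitters are 25×0.12 = 3.0 to 25×0.20 = 5.0 on mHealth, and 25×0.05 = 1.25 to 25×0.10 = 2.5 on control. The expected difference runs from 3.0−2.5 = 0.5 to 5.0−1.25 = 3.75. Its standard deviation is √{25[p1(1−p1)+p2(1−p2)]}, from √{25(0.1056+0.0475)} = 1.96 (12% v 5%) to √{25(0.16+0.09)} = 2.50 (20% v 10%).

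**3. What a yes to the pharmacotherapy question means.** Let c be the share using the study lozenge and o the share using outside medication, taken as independent. Neither is in the document; I assume c = 60%-100% and o = 5%-20%. Then P(yes) = c + (1−c)o, and the share of yes answers with outside use is o/P(yes).

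- c = 0.6, o = 0.05: P(yes) = 0.62, share 0.08
- c = 0.6, o = 0.20: P(yes) = 0.68, share 0.29
- c = 0.8, o = 0.05: P(yes) = 0.81, share 0.06
- c = 0.8, o = 0.20: P(yes) = 0.84, share 0.24
- c = 1.0: P(yes) = 1.00, share equal to o (0.05-0.20)

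A true between-arm gap in outside use shrinks by the factor (1−c). A gap of 20% v 5% (15 points) appears as 68−62 = 6 points at c = 0.6, 84−81 = 3 points at c = 0.8, and 0 at c = 1. If lozenge uptake differs by arm, that difference is mixed in too.

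**4. Does the recall period rescue the item?** None is stated. If the question means any use during the study, study lozenges count. If it means current use at follow-up, the answer depends on how long lozenges last. On the abrupt-quit path, counting from the start of messages, the quit date falls in weeks 2-4. A 4-week supply then ends at weeks 6-8, and the 12-week instruction ends at weeks 14-16. Follow-up is 30 days (4.3 weeks) after messages end: about week 12.3 if messages last 8 weeks (Abrupt Cessation), or week 14.3 if they last ten (Text-based Cessation Support). So a participant following the 12-week instruction could still be using lozenges at follow-up, some of them possibly obtained elsewhere.

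**5. Imbalance at entry.** The number already in treatment is not given; I assume 5 or 10 of 50. With a 25/25 split, the number k falling in one arm is hypergeometric.

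- 5 of 50: P(gap ≥ 3) = 2[C(25,5) + 25·C(25,4)]/C(50,5) = 2(53,130 + 316,250)/2,118,760 = 0.35
- 10 of 50: P(gap ≥ 4) = 0.29, by the same method

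If outside treatment raised the quit rate from 10% to 20%-30% (assumed), a gap of 3 shifts the difference by 3×0.1 to 3×0.2 = 0.3 to 0.6 quitters (1.2-2.4 points). A gap of 4 shifts it by 0.4 to 0.8 quitters (1.6-3.2 points). The planned differences are 2 to 15 points.

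**The case against.** The strongest reply is that little depends on this item. Allocation is randomised, so treatment at entry can differ between arms only by chance, like any unmeasured covariate. Treatment taken up afterwards is part of what the intention-to-treat comparison estimates. Feasibility and acceptability are the primary outcomes, and efficacy is described as exploratory. The shift in step 5 is small beside a chance standard deviation of 2.0 to 2.5 quitters. All of that stands.

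It is also fair that the surveys are not in the document. The tobacco history list is introduced as examples, and the Cessation Resources paragraph summarises a topic without giving item wording. The finding is that the plan specifies no such baseline question and no separation of study lozenges; the forms may already do better.

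Nor is the whole item uninformative. Public services and physician support are not confused with the lozenge and lack only timing. Below full lozenge uptake, a no still rules out outside medication.

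What the reply does not answer is that a descriptive item should describe what it names. In addition, follow-up answers will be missing for dropouts. The 80% retention target allows 50×0.20 = 10 of them, all counted as non-quitters. A baseline question would be available for everyone.

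**Conclusion.** The point holds as a measurement gap. As specified, the pharmacotherapy answer says little about outside medication by arm, and nothing at all if every participant uses the study lozenge. No listed measure shows whether outside help of any kind began before or after randomisation. The 5%-29% range rests on assumed uptake and outside-use rates, and the 0.3-0.8 quitter range on assumed prevalence and effect.

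A reader might infer more, and the document does not support it:

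- *The efficacy comparison is biased.* It is not, by design; only chance imbalance at entry remains.
- *One or two quits owed to outside treatment would make or erase the trend.* The document gives no prevalence or effect from which to show this, and the assumed cases stay below one quitter.
- *People already in treatment should be excluded.* That is an eligibility choice for the sponsor to make and state. Broad entry is defensible in a feasibility pilot, and an exclusion could work against the target of 50 enrolled in 4 months.

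This is a cheap improvement to how a small difference in quit counts can be read. It is not a flaw that invalidates the pilot.

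**What to change.** 1. Add one baseline question on current use of any cessation medication, nicotine replacement or cessation program.
2. Split the follow-up item into (a) use of the study-supplied lozenge and (b) use of any cessation medication the study did not supply, with its source and whether it began before or after enrolment. Ask the same timing question for public services and physician support, and state the recall period.
3. Report the baseline answer and both follow-up parts by arm beside the quit rates, as description only.
4. Have the sponsor state whether people already in treatment are eligible.
5. Reconcile the 4-week supply with the 12-week use instruction in the Nicotine Replacement Therapy paragraphs of both arms. Until that is done, lozenges obtained elsewhere to follow the instruction will blur the split in item 2.

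The cost is a few extra questions in surveys already planned. Sample size, randomisation and the planned tests are unchanged.
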